12 DATA REPORTING / REGULATORY REQUIREMENTS

Adverse event lists, guidelines, and instructions for AE reporting can be found in Section 10.0 (Adverse Events: List and Reporting Requirements). The Data Safety Monitoring Plan is described in Section 14.3.

12.1 Data Collection

The Herbert Irving Comprehensive Cancer Center has an electronic clinical trials and data management system (CTMS) that will be used for data collection. CRFs for the study will be built into the CTMS for data entry. The system has full auditing capabilities which is web-based and housed on a server in a fully HIPAA compliant server room with restricted access and video

camera monitoring. All users must login with their own application username and password. Users off campus must first access the Virtual Private Network with their assigned campus username and password and then use their application credentials. Users are only able to see study information if they are indicated as study personnel in our electronic IRB system. Users are limited to access based on the role assigned in their corresponding protocol. Subject data is entered directly into the system, which (in the case of Columbia subjects) confirms the correct identity of patients via an interface with the electronic medical patient index. Staff with the appropriate IRB defined roles can run reports within the system for reporting purposes.

12.2 Data Reporting

Case Report Forms will be completed for each subject enrolled into the clinical study through the CTMS. It is the investigator's responsibility for ensuring that all clinical and laboratory data entered on the corresponding CRFs are complete, accurate and authentic.

12.3 Data and Safety Monitoring Committee

The NCI-approved Data Safety and Monitoring Committee (DSMC) of the Herbert Irving Comprehensive Cancer Center (HICCC) will monitor every subject who receives treatment on this protocol for toxicity. This protocol will adhere to the policies of the currently approved HICCC Data and Safety Monitoring Plan (DSMP), which is in accordance with NCI and CUMC-IRB policy and guidelines. The committee chair is appointed by the HICCC Director. The committee consists of HICCC faculty and staff with expertise in oncology, research pharmacy, research nursing, and data management. The DSMC convenes twice a month to review patient safety and the conduct of the trial. The PI will submit data and safety monitoring reports to the DSMC at a frequency to be determined by the DSMC based on risk to the subjects.

At the time of renewal, the study team will submit the most recent DSMC approval letter for safety review to the CUMC IRB. Any modifications that are required by the DSMC to ensure patient safety will be submitted to the IRB. All protocol deviations, violations, and eligibility waivers will be submitted to and approved by the DSMC prior to being reported to the IRB. All study data reviewed and discussed during these meetings will be kept confidential.

12.4 Quality Control and Quality Assurance

Independent monitoring of the clinical study for protocol and GCP compliance will be conducted periodically by the CPDM Compliance Core on behalf of the HICCC DSMC. Additionally, the Compliance Oversight Committee of the IRB at Columbia University Medical Center may audit the study at any time per institutional policies and procedures. The investigator-sponsor and Columbia University Medical Center will permit direct access of the study monitors and appropriate regulatory authorities to the study data and to the corresponding source data and documents to verify the accuracy of this data.

A risk-based approach will be used by the Compliance Core to determine the frequency, number of subject charts, and data elements to be monitored. The Compliance Coordinator will review the

study status and summarize enrollment, toxicities, SAEs/UPs, dose escalation, statistical endpoints (e.g., stopping rules), etc. for the full DSMC membership at the regularly scheduled meetings.

Internal On-site Monitoring:

- Initial, recurrent, and close-out on-site monitoring visits will also be conducted at remote clinical sites, as appropriate/feasible. Other sites will have monitoring performed remotely (see below for further details).
- The Compliance Coordinator will communicate with the site coordinator/Site Principle Investigator to schedule the monitoring visit and arrange for access to study materials and documentation.
- The assigned Compliance Coordinator will monitor IIT trials within 1 month after the first subject is enrolled and throughout the life of the study to ensure that the study is being conducted in accordance with the protocol, GCP, applicable federal and local regulations, and per all applicable SOPs. The Compliance Coordinator is responsible to notify the PI and CRNP/CRN/CRC of upcoming monitor visits and convey what information and documentation will be required for the visit(s). The Compliance Coordinator is responsible for verifying that informed consent is properly obtained, eligibility is met (via the central registration process), and all study procedures are conducted according to the study protocol. The Compliance Coordinator will also verify that the data reported in the CRF's accurately reflect source documents, that all toxicities have been reported to date, and that all SAE's/UPs/deviations/violations have been reported according to local IRB and HICCC DSMC requirements. The Compliance Coordinator will issue queries and ensure resolution in a timely and efficient manner. The Compliance Coordinator will also monitor for applicable regulatory compliance and research pharmacy compliance (if applicable) and communicate any deficiencies as appropriate.

12.5 Confidentiality

Information about study subjects will be kept confidential and managed according to the requirements of the Health Insurance Portability and Accountability Act (HIPAA). Those regulations require a signed subject authorization informing the subject of the following:

- What protected health information (PHI) will be collected from subjects in this study
- Who will have access to that information and why
- Who will use or disclose that information
- The rights of a research subject to revoke their authorization for use of their PHI.

In the event that a subject revokes authorization to collect or use PHI, the investigator, by regulation, retains the ability to use all information collected prior to the revocation of subject authorization. For subjects that have revoked authorization to collect or use PHI, attempts should be made to obtain permission to collect at least vital status (e.g., that the subject is alive) at the end of their scheduled study period.

The subject binders will be maintained within the CPDM offices, a secured floor within the Herbert Irving Pavilion and only the investigator and study staff will have access to the file.

12.6 Source Documents

Source data is all information, original records of clinical findings, observations, or other activities in a clinical trial necessary for the reconstruction and evaluation of the trial. Source data are contained in source documents Examples of these original documents, and data records include: hospital records, clinical and office charts, laboratory notes, memoranda, subjects' diaries or evaluation checklists, pharmacy dispensing records, recorded data from automated instruments, copies or transcriptions certified after verification as being accurate and complete, microfiches, photographic negatives, microfilm or magnetic media, x-rays, subject files, and records kept at the pharmacy, at the laboratories, and at medico-technical departments involved in the clinical trial.

12.7 Case Report Forms

The study case report form (CRF) is the primary data collection instrument for the study. All data requested on the CRF must be recorded. All missing data must be explained. If a space on the CRF is left blank because the procedure was not done or the question was not asked, write "N/D". If the item is not applicable to the individual case, write "N/A".

12.8 Records Retention

Records relating to a specific research activity, including research records collected by investigators, must be maintained for at least three years after completion of the research (45 CFR 46.115(b); 21 CFR 56.115(b); 21 CFR 312.62). This minimum retention period applies whether or not any subjects were enrolled in the study. If the research is FDA regulated, records should be retained for at least two years after approval of the investigational agent by FDA; if it is not approved, records should be retained at least two years after the study is terminated and FDA is notified (note the additional requirement below for clinical research studies); Clinical records, including consent forms that document clinical intervention or clinical diagnostic procedure research-related procedures, must be retained in medical records by the institution for at least seven years, per CUMC and NYP policy which is based on state law.

13 STATISTICAL CONSIDERATIONS

13.1 Study Design and Sample Size

This study is a single-center, randomized open-label phase 2 trial to evaluate the efficacy and safety of anti-IL-8 in hospitalized adults with severe or critical COVID-19. The primary endpoint is time to improvement in clinical status: the time (days) required from the start of treatment to the improvement of clinical status (2 points) assessment from baseline based on the 7-point ordinal scale. Patients for whom there was no event will be censored.

Patients will be randomized in a 2:1 allocation ratio to either anti-IL-8 or standard of care. Patients will be assessed daily while hospitalized. Discharged patients will be contacted by telephone on Day 29 and then monthly up to one-year to assess status. In addition to these specific assessment times, one interim analysis is planned at and the DSMC will actively monitor interim data to make recommendations about early signs of overwhelming efficacy and futility/study closure (see Section 13.4.)

With a sample size of 138 patients: N=92 patients randomized to the treatment arm and N=46 patients assigned to the standard of arm/control, the study will have 80% power to detect an increase in median time to improvement from 2 days (control) to 5 days (treatment arm) with one-sided alpha of 0.025. The sample size was estimated based on a hazard ratio (HR) of 0.40 assuming an exponential survival distribution with inflation to account for one interim look and 5% drop-out rate.

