Statistical Methodology	This is a single center, randomized, open-label, phase 2 trial to evaluate the time-to-improvement in the 7 point ordinal scale following treatment with BMS-986253 compared to standard of care in hospitalized patients with COVID-19 respiratory disease. With a sample of 138 patients (N=92 patients randomized to the treatment arm and N=46 patients assigned to the control/standard of care arm), the study will have 80% power to detect an increase in the median time to improvement from 5 days (control) to 2 days (anti-IL-8 arm) with one-sided alpha of 0.025. The sample size was estimated based on a hazard ratio (HR) of 0.40 assuming an exponential survival.
Interim Analysis	One interim analysis is planned once 17 (40% of the total 41 events) have been observed using O'Brien and Fleming stopping boundary using the Lan-DeMets spending function and inflation for drop-outs. The intent-to-treat (ITT) principle is applied to the analysis, and therefore, we inflated the sample size by 5% to safeguard against drop-outs/lost-to-follow-up.

Protocol Schema:

Contents

Protocol Signature Page	4
1. Introduction	12
2. Study Objectives	12
Primary Objective	12
Secondary Objectives.....	12
2.1 Exploratory Objectives	13
3. Background	13
3.1 Disease Background.....	13
3.2. IL-8 is a key cytokine in the pathogenesis of coronavirus-associated ARDS.....	14
3.3. Rationale for anti-IL-8 therapy in hospitalized patients with severe COVID-19.....	15
Investigational AgentS	15
3.4 BMS-986253	15
4. Study Design	20
4.1 General Design.....	20
4.2 Number of Subjects.....	21
5. Subject Selection and Withdrawal	21
5.1 Inclusion Criteria	21
5.2 Exclusion Criteria	23
5.3 Inclusion of Women and Minorities	23
5.4 Subject Recruitment.....	23
5.5 Early Withdrawal of Subjects	24
6. REGISTRATION PROCEDURES	25
6.1 CUMC Research Participant Registration	25
6.2 Informed Consent Procedures.....	26
7. TREATMENT PLAN	27
7.1 Agent Administration.....	27
7.2 Management of Infusion Reactions:	28
7.3 General Concomitant Medication and Supportive Care Guidelines	29
7.4 Treatment Compliance.....	29
7.5 Randomization and Blinding	29
7.6 Duration of Therapy.....	30
7.7 Duration of Follow Up.....	30
7.8 Criteria for Removal from Study	30
DOSING DELAYS/ DOSE MODIFICATIONS.....	30
7.9 Criteria and Procedures for Dose Modifications and Interruptions	30

8.	ADVERSE EVENTS: LIST AND REPORTING REQUIREMENTS	32
8.1	Adverse events	32
8.2	Definitions.....	33

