13.2 Study Endpoints and Analysis Plan

All subjects who receive at least one dose of study drug will be considered evaluable and included in the efficacy and safety analysis.

Analytic plan for primary objective:

The primary efficacy null hypothesis of the equality of time to improvement (2 points) in clinical status curves will be tested with the log-rank test. The overall type I error for the primary analysis will be considered one-sided alpha of 0.025. Kaplan-Meier estimates will be reported for each of the two arms with median time to improvement and 95% confidence intervals (CI). Cox regression will be employed to estimate the treatment effect (HR) and 95% CI.

Analytic plan for secondary and exploratory objective:

We will estimate the distributions of all time-to-event endpoints using the Kaplan-Meier method and if possible, provide medians (95% CI). Comparisons between survival curves will be assessed using log-rank tests and Cox regression models.

For each arm, we will estimate the 1-month mortality rate and incidence of adverse events graded by CTCAE v5.0 using the exact 95% confidence intervals. Comparisons between the two arms will be assessed using chi-squared or Fisher's exact tests. The mean/medians of the 7-point ordinal scores at day 14 after the start of treatment will be computed and compared between the two groups using two-sample t-test or the equivalent non-parametric Wilcoxon Rank-Sum test if normality is not satisfied.

Changes in exploratory endpoints (before and after treatment) will be quantified using means (95% CI) and/or medians (inter-quartile ranges) for non-normal data. Comparisons between the two arms will be made using two-sample independent t-tests or the non-parametric equivalent, Wilcoxon Rank-Sum test. The associations between baseline levels and/or changes over time of IL-8 and other key cytokines (TNF, IL-1b, IL-6) with outcomes will be assessed using regression models.

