13.4 Interim analyses

One interim analysis is planned after approximately 17 (40% of the total 41 events) have been observed using O'Brien and Fleming stopping boundary using the Lan-DeMets spending function at a nominal type I error of 0.025. The intent-to-treat (ITT) principle is applied to the analysis, and therefore, we inflated the sample size by 5% to safeguard against drop-outs.

An independent Data Safety Monitoring Committee (DSMC) will serve as the primary reviewer of the results of the interim analyses of the study and will make recommendations for discontinuation of the study or protocol modifications. Stopping rules for overwhelming efficacy and/or futility are provided in Table 4 below.

Table 4. Efficacy and Boundaries and Properties for the Time to Improvement Analysis

Analysis*	Value	Efficacy	Futility
IA1: 40%	Nominal critical point Z-value	3.3569	0.0811
N: 138	p (1-sided)	0.0004	0.4677
Events: 17	~HR at bound	0.1720	0.9584
Month: 2.6	P(Cross) if HR=1	0.0004	0.5323
	P(Cross) if HR=0.4	0.0599	0.0427
IA2: 100%	Nominal critical point Z-value	1.9622	1.9622
N: 138	p (1-sided)	0.0249	0.0249
Events: 41	~HR at bound	0.5217	0.5217
Month: 7	P(Cross) if HR=1	0.0240	0.9760
	P(Cross) if HR=0.4	0.8000	0.2000

*This column displays the number of events and percentage (%) of needed time to improvement events, the expected sample size (N), and the estimated months (Month) after first participant is randomized for each analysis.

p (1-sided): the nominal α for testing.

~HR at bound: the approximate hazard ratio required to reach the bound for overwhelming efficacy or futility stop.

P (Cross if HR=1): the probability of crossing a bound at or before each analysis under the null hypothesis.

P (Cross if HR=0.40): the probability of crossing a bound at or before each analysis under the alternative hypothesis.

Abbreviations: HR = hazard ratio; IA = interim analysis.

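### The synopsis and 13.1 power the primary test in opposite directions with the same HR of 0.40, and Table 4 never says which way its HR or Z runs

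*Combined protocol and SAP*

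**What the plan says.** The primary endpoint is the time from start of treatment to a 2-point improvement on the ordinal scale (sections 11.1 and 13.1), tested by log-rank at one-sided alpha 0.025 (13.2).

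- **Section 13.1** claims 80% power to "detect an increase in median time to improvement from 2 days (control) to 5 days (treatment arm"), and adds: "The sample size was estimated based on a hazard ratio (HR) of 0.40 assuming an exponential survival distribution".
- **Synopsis, Statistical Methodology** claims 80% power for an "increase in the median time to improvement from 5 days (control) to 2 days (anti-IL-8 arm"), and adds: "The sample size was estimated based on a hazard ratio (HR) of 0.40 assuming an exponential survival".
- **Section 13.2** says "Cox regression will be employed to estimate the treatment effect (HR) and 95% CI". It names no reference arm.
- **Section 13.4, Table 4** gives efficacy bounds at HR 0.1720 (interim, Z 3.3569) and 0.5217 (final, Z 1.9622), an interim futility bound at HR 0.9584 (Z 0.0811), and crossing probabilities for HR=0.4. Its note explains the HR row only as "the approximate hazard ratio required to reach the bound for overwhelming efficacy or futility stop". Both rows show N=138, with 17 events at month 2.6 and 41 at month 7; the note describes these columns as "the expected sample size (N), and the estimated months (Month) after first participant is randomized for each analysis".
- **Section 13.4** also says that the DSMC reviews the interim results and "will make recommendations for discontinuation of the study or protocol modifications".

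**The concern.** The event is a good one. Benefit means a shorter time to improvement, hence an anti-IL-8:control hazard ratio above 1. Taken literally, 13.1 powers a one-sided test for delayed recovery on the drug. The synopsis medians describe benefit, but the word used for the change is wrong, and the HR matches only if control is the numerator.

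Table 4 does not settle the matter. Section 13.2 calls the HR the treatment effect, which most readers would take as treatment over control, and 13.1's own medians give 0.40 in exactly that orientation. A committee using Table 4 that way would be pointed towards futility for a drug that speeds recovery and towards efficacy for one that slows it. The direction of the final one-sided test is equally undefined, because 13.2 states only a null of equal curves.

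The table's calendar raises a linked doubt. With medians in days, 41 events arrive long before 138 patients are enrolled under staggered accrual. It is therefore unclear whether the final analysis comes at 41 events or after all 138 have been followed, and power differs greatly between the two.

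**Working it through.** **Inputs from the documents.** Medians 5 and 2 days (synopsis) or 2 and 5 days (13.1), control first; HR 0.40; one-sided alpha 0.025; power 80%; allocation 2:1; 41 events with the interim at 40%; Table 4 Z-bounds.

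**Assumptions added.** Exponential times; true medians 5 days (control) and 2 days (anti-IL-8); randomization in blocks of 3; accrual over 79, 213 or 365 days, or instantaneous (79 and 213 days are months 2.6 and 7); censoring at day 28 unless noted.

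**1. Reproducing the plan's figures.**
- Schoenfeld events: (1.960 + 0.842)² / [(2/9)(ln 0.40)²] = 7.849 / (0.2222 × 0.8396) = 42.1, close to 41.
- Power at 41 events: Φ(0.9163 × √(41 × 2/9) − 1.960) = Φ(0.806) = 0.79 for a single look, and 0.777 with the interim.
- Lan-DeMets O'Brien-Fleming spending at 0.40 is 0.000394, so Z = 3.3569.
- HR at bound = exp(−Z/√(D × 2/9)). With D = 0.40 × 41 = 16.4: exp(−3.3569/1.909) = 0.172 and exp(−0.0811/1.909) = 0.958. With D = 41: exp(−1.9622/3.019) = 0.522.

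The table is internally sound, and in it a positive Z means HR below 1. Schoenfeld's formula uses only |ln HR|, so its event count is the same for 0.40 and 2.5.

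**2. Direction.** Under exponential times, the anti-IL-8:control HR is the control median divided by the anti-IL-8 median.
- Synopsis: 5/2 = 2.5, so 0.40 is control:anti-IL-8.
- Section 13.1: 2/5 = 0.40, so 0.40 is anti-IL-8:control.

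**3. Table 4 under each reading, when the drug works (5 vs 2 days).** Group-sequential log-rank simulation, 6,000 runs (3,000 with whole-day times).
- *Read as anti-IL-8:control.* Interim futility is crossed in 95.4%, 95.2%, 95.2% and 95.0% of runs (79, 213, 365 days, instant), and in 94.3–94.9% without day-28 censoring. Efficacy is crossed in at most 0.02%. Analytic check: mean Z = −0.9163 × 1.909 = −1.749, and P(Z < 0.0811) = Φ(1.830) = 0.966.
- *Read as control:anti-IL-8, final analysis at 41 events.* Power is 71.3%, 70.8%, 70.5% and 67.1% for the same accruals; 71.8% and 71.0% without day-28 censoring; 72.2% and 72.9% with whole-day times (79 and 213 days in both cases).
- *For comparison, the 13.1 direction (2 vs 5 days) with the rule as printed.* 77.3%, 77.6% and 83.4% (79 days, 213 days, instant).

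**4. Events against N and calendar time.**
- Mean enrolment at the 41st event is 48.5, 43.9 and 42.8 patients (79, 213, 365 days); with whole-day times, 49.3 and 44.3 (79 and 213 days).
- All 138 followed to day 28: 92 × (1 − 2^(−14)) + 46 × (1 − 2^(−5.6)) ≈ 92.0 + 45.1 = 137 events, with simulated power 99.8%.
- Uniform accrual of 138 over 2.6 months (79 days): the fraction with an event in each arm is about 1 − 1/(λ × 79), where λ = ln 2/median. For the synopsis medians this is 92 × 0.9635 + 46 × 0.909 ≈ 130 events; for the 13.1 medians, about 127–128. Table 4 shows 17.
- Uniform accrual over 7 months: about 47–49 events at month 2.6 and 133–135 at month 7. Table 4 shows 17 and 41.

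**The case against.** The best defence is that the intention is easy to infer. The objective is improvement, Table 4 labels its columns efficacy and futility and treats HR 0.40 as the alternative, and the synopsis medians give 0.40 only as control:anti-IL-8. On that view no DSMC would call faster recovery futile. Calling the 13.2 HR treatment:control is also an inference, since no numerator is named there. This has force on likelihood: the 94–95% figure is conditional on a misreading. It does not remove the contradiction. The main statistical section states the opposite medians, and they support the harmful reading. A one-sided test and its stopping bounds should not need to be inferred.

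On power, 41 events does reproduce by the usual formula, and the gap between 79% and 70–73% reflects simulation against an asymptotic approximation. That stands: the gap is not by itself an error in the plan.

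The event trigger could be said to be given, since Table 4's final row is at 41 events. But the same row carries N=138 and month 7, which do not fit medians in days.

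Reciprocals of the printed bounds may also not be what a proper rerun yields. A Lachin-Foulkes type calculation (assumed medians of 2 or 5 months, 7-month study, accrual over 1–6 months, dropout hazard 0–0.05 per month) needs 43.2–45.8 events when the larger arm improves faster, against 40.3–41.1 when it improves more slowly. The printed 41 thus sits closer to the 13.1 direction. This is only suggestive, because the plan does not give its software or accrual inputs, but it is a reason to rerun the design and not merely relabel it.

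**Conclusion.** The concern holds and must be fixed. The contradiction in the medians, the wrong word for a beneficial change and the undefined HR and Z are plain on the page and need no assumptions. As written, 13.1 powers the primary test for slower recovery on anti-IL-8.

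The size of the consequence depends on the reading. If Table 4 is taken as anti-IL-8:control and the true medians are 5 and 2 days with exponential times, interim futility is crossed with probability 94–95% and efficacy almost never. If it is taken as control:anti-IL-8, the rule works, with simulated power at 41 events of 70–73% under staggered accrual and 67% if all enrol at once; Schoenfeld gives 78–79%. That shortfall from 80% is method-dependent and secondary.

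The mismatch between 41 events, N=138 and months 2.6 and 7 holds for the stated medians in either direction. It leaves open whether the final analysis involves about 43–49 enrolled patients or all 138, where power would exceed 99%.

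**What to change.** 1. **Synopsis and 13.1:** state one hypothesis, a decrease in median time to improvement from 5 days (control) to 2 days (anti-IL-8), with HR for improvement (anti-IL-8:control) = 2.5 and one-sided alpha 0.025.
2. **13.2 and 13.4:** define HR as anti-IL-8:control and positive Z as faster improvement on anti-IL-8, for both the interim and the final test.
3. **Table 4:** rerun the group-sequential calculation for HR 2.5 with 2:1 allocation and restate the bounds. As a guide:
   - If 41 events is kept: efficacy at about HR ≥ 5.80 (interim) and ≥ 1.92 (final), futility at about ≤ 1.04. The 5.80 uses 16.4 interim events; exactly 17 gives exp(3.3569/√(17 × 2/9)) = 5.62. Restate power with its method and accrual assumptions.
   - If 80% power is kept: about 50 events with the interim look under staggered accrual (simulated power 80.1% and 79.8% for 79 and 213 days, 8,000 runs). With the same Z-values the bounds are about 4.92, 1.80 and 1.04. These are illustrative, since the futility bound should be recomputed for the new design.
4. **Timing:** reconcile the event counts and months with N=138, and say whether the final analysis is triggered by events or by all 138 completing follow-up.

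The cost is wording in three places, one table and one rerun. The stated power at 41 events may come out lower. A target of about 50 events would move the final analysis from about 43–49 to about 53–58 enrolled patients, well within 138.
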